6.2.2 Follow-up for toxicities

Patients who complete study drug or whose study drug is interrupted or permanently discontinued due to an AE must be followed at least once a week for 4 weeks, and then at 4-week intervals until resolution or stabilization of the event. All patients will be followed for onset of any new serious adverse events for 30 days following the last dose of study treatment.

6.2.3 Anticipated risks and safety concerns of the study drug

Appropriate eligibility criteria as well as specific dose modification and stopping rules are included in this protocol.

6.3 Concomitant medications

6.3.1 Permitted concomitant therapy

Medications required to treat AEs, manage cancer symptoms, concurrent diseases and supportive care agents, such as packed red blood cells (PRBC), pain medications, anti-emetics and anti-diarrheals are allowed. Hematopoietic growth colony stimulating factors may be used therapeutically or as secondary prophylaxis, see [Appendix 4](#).

The patient (patient's guardian if appropriate) must be instructed to notify the treating physician of new medications after the start of the study drug. All medications (other than study drug) and significant non-drug therapies (including blood transfusions and physical therapy) administered within 30 days of first dose of study drug and during the study must be listed on the Concomitant Medications/Significant Non-Drug therapies eCRF as appropriate. Patients taking concomitant medications chronically should be maintained on the same dose and dosing schedule throughout the study, as medically feasible.

6.3.2 Permitted concomitant therapy requiring caution

The following therapies are permitted in this study; however, they should be used with caution:

- Moderate inhibitors or inducers of CYP3A4/5
- Sensitive substrates of CYP3A4/5 with wide therapeutic index
- Known inhibitors of BSEP
- Sensitive substrates of the renal transporters, MATE1 and OCT2, and sensitive substrates of BCRP
- Medications that carry a possible risk for QT prolongation

6.3.3 Prohibited concomitant therapy

The following medications are prohibited during treatment in this study ([Appendix 4](#)):

- Strong inhibitors or inducers of CYP3A4/5
- Substrates of CYP3A4/5 with narrow therapeutic index

- Medications with a known risk for QT prolongation
- Other investigational and antineoplastic therapies
- Herbal medications
- Primary prophylactic hematopoietic growth factors
- Palliative radiotherapy
- Patients must avoid consumption of grapefruit, grapefruit hybrids, pummelos, star-fruit, Seville oranges or products containing the juice of each during the entire study and preferably for an additional 7 days before the first dose of study medications, due to potential CYP3A interaction with the study medications. Orange juice is allowed.

Refer to the LEE011 Investigator's Brochure and [Appendix 4](#) for information on possible interactions with other drugs.

6.4 Patient numbering, treatment assignment or randomization

6.4.1 Patient numbering

Each patient is identified in the study by a Patient Number (Patient No.), that is assigned when the patient is first enrolled for screening and is retained as the primary identifier for the patient throughout his/her entire participation in the trial. The Patient No. consists of the Center Number (Center No.) (as assigned by Novartis to the investigative site) with a sequential patient number suffixed to it, so that each patient is numbered uniquely across the entire database. Upon signing the informed consent form, the patient is assigned to the next sequential Patient No. available to the investigator through the Oracle Clinical RDC interface.

[figure not shown]
The investigator or designated staff will contact the IRT and provide the requested identifying information for the patient to register them into the IRT. Once assigned, the Patient No. must not be reused for any other patient and the Patient No. for that individual must not be changed even if the patient is re-screened. If the patient fails to be randomized or start treatment for any reason, the reason will be entered into the Screening Disposition eCRF.

IRT must be notified within 2 days of a patient screen failure.

6.4.2 Treatment assignment or randomization

Patients will be randomized to 1 of the 2 treatment arms in a 2:1 ratio. LEE011 and placebo will be supplied to investigational sites by Novartis or its designee as hard gelatin capsules (200 mg) as individual patient supply packaged in bottles. Storage conditions are described on the medication label.

Block randomization will be used to allocate patients between treatment arms. The randomization numbers will be generated using the following procedure to ensure that treatment assignment is unbiased and concealed from patients and investigator staff. A patient randomization list will be produced by the Interactive Response Technology (IRT) provider using a validated system that automates the random assignment of patient numbers to randomization numbers. These randomization numbers are linked to the different treatment arms, which in turn are linked to medication numbers. A separate medication randomization list will be produced by or under the responsibility of Novartis Drug Supply Management

using a validated system that automates the random assignment of medication numbers to medication packs containing each of the study treatments.

Prior to dosing, all patients who fulfill all inclusion/exclusion criteria will be randomized via IRT to one of the treatment arms. The investigator or his/her delegate will call or log on to the IRT and confirm that the patient fulfills all the inclusion/exclusion criteria. The IRT will assign a randomization number to the patient, which will be used to link the patient to a treatment arm and will specify a unique medication number for the first package of study drug to be dispensed to the patient. The randomization number will not be communicated to the caller.

For patient's crossing over to LEE011, the investigator or his/her designee will call or log on to the IRT and confirm that the patient fulfills the criteria to crossover. The IRT will assign a unique medication number for the study drug to be dispensed to the patient.

The medication label will be in the local language and comply with the legal requirements of each country. The study drug packaging has a 2-part label. A unique medication number is printed on each part of this label which corresponds to one of the treatment arms and a dose level. Responsible site personnel will identify the study drug package(s) to dispense to the patient by using the IRT and obtaining the medication number(s). Site personnel will add the patient number on the label. Immediately before dispensing the package to the patient, site personnel will detach the outer part of the label from the packaging and affix it to the source document (Drug Label Form) for that patient's unique patient number.

The investigator or responsible site personnel must instruct the patient or caregiver to take the study drug as per protocol. Study drug will be dispensed to the patient by authorized site personnel only. All dosages prescribed to the patient and all dose changes during the study must be recorded on the Dosage Administration Record eCRF.

6.4.3 Drug supply and storage

Study drug will be centrally supplied by Novartis DSM or a Novartis designated CRO, and must be received by a designated person at the study site, handled and stored safely and properly, and kept in a secured location to which only the investigator and designated assistants have access. Upon receipt, the study drugs should be stored according to the instructions specified on the drug labels and in the Investigator's Brochure.

[figure not shown]
6.4.4 Study drug compliance and accountability

6.4.4.1 Study drug compliance

Compliance will be assessed by the investigator or study personnel at each patient visit and information provided by the patient or caregiver will be captured in the Drug Accountability eCRF. This information must be captured in the source document at each patient visit.

6.4.4.2 Study drug accountability

The investigator or designee must maintain an accurate record of the shipment and dispensing of study drug in a drug accountability log. Drug accountability will be noted by the field monitor during site visits and at the completion of the study. Patients will be asked to return

all unused study drug and packaging on a regular basis, at the end of the study and at the time of study drug discontinuation.

At study close-out and as appropriate during the course of the study, the investigator will return all used and unused study treatment, packaging, drug labels, and a copy of the completed drug accountability log to the Novartis monitor or to the Novartis address provided in the investigator folder at each site.

6.4.4.3 Handling of other study treatment

Not applicable.

6.4.5 Disposal and destruction

The study drug supply can be destroyed at the local Novartis facility by the, Drug Supply group or third party, as appropriate. Drug supply is to be destroyed at the site only if permitted by local regulations and authorized by Novartis.

7 Visit schedule and assessments

7.1 Study flow and visit schedule

Table 7-1 lists all of the assessments and indicates with an “X”, the visits when they are performed. All data obtained from these assessments must be supported in the patient’s source documentation.

No eCRF will be used as a source document.

[figure not shown]
After the screening period, all assessments have a ± 3 day window unless otherwise indicated

If study drug is being held due to toxicity, then the scheduled visits and assessments should still be performed per protocol, unless otherwise specified. Additional assessments may be performed as clinically indicated.

[REDACTED]

Table 7-1 Visit evaluation schedule

	Category	Protocol Section	Screening	Treatment Cycles							EOT	Crossover cycles						Crossover EOT	Follow-Ups				
				Cycle 1				Cycle 2		Subsequent Cycles		Cycle 1				Cycle 2			Subsequent Cycles	30-Day	Progression	Survival	
				1	8	15	21	1	21			1	8	15	21	1	21						1
Day of cycle			-14 to-1	1	8	15	21	1	21	1		1	8	15	21	1	21	1					
Obtain informed consent	D	7.1.1	X																				
IVRS/IRT registration	D	4.1	X																				
Demography	D	7.1.1.3	X																				
Inclusion/exclusion criteria	D	5.2 / 5.3	X									X											
Medical history	D	7.1.1.3	X																				
Diagnosis and extent of cancer	D	7.1.1.3	X																				
Prior antineoplastic therapy	D	7.1.1.3	X																				
Physical examination	S	7.2.2.1	X	X	X	X	X	X		X	X	X	X	X	X			X					
ECOG performance status	D	7.2.2.4	X	X				X		X	X	X			X		X	X					
Height	D	7.2.2.3	X																				
Weight	D	7.2.2.3	X	X				X		X	X	X			X		X	X					
Vital signs	D	7.2.2.2	X	X	X	X	X	X	X	X	X	X	X	X	X	X	X	X	X				

	Category	Protocol Section	Screening	Treatment Cycles							EOT	Crossover cycles						Crossover EOT	Follow-Ups				
				Cycle 1				Cycle 2				Subsequent Cycles	Cycle 1				Cycle 2		Subsequent Cycles	30-Day	Progression	Survival	
				1	8	15	21	1	21	1			1	8	15	21	1						21
Day of cycle			-14 to-1	1	8	15	21	1	21	1		1	8	15	21	1	21	1					
Hematology	D	7.2.2.5.1	X	X		X	X	X	X	X	X	X		X	X	X		X	X				
Chemistry	D	7.2.2.5.2	X	X		X	X	X	X	X	X	X		X	X	X		X	X				
Thyroid panel	D	7.2.2.5.3	X								X							X					
Coagulation	D	7.2.2.5.4	X								X							X					
Pregnancy test	D	7.2.2.5.5	X	X				X		X	X	X				X		X	X				
ECG	D	7.2.2.6.1	X	X	X	X		X	X	X	X	X	X		X	X	X	X					
Cardiac imaging (MUGA/ECHO)	D	7.2.2.6.2	X								X							X					
Collection of archival paraffin blocks/slides or newly obtained tumor sample	D	7.2.4.1	X																				
Tumor assessments	D	7.2.1	X	Every 8 weeks for first 12 months from C1D1, then every 12 weeks							X	Every 8 weeks for the first 12 months from C1D1, then every 12						X		X			

[Redacted text block]

	Category	Protocol Section	Screening	Treatment Cycles							EOT	Crossover cycles						Crossover EOT	Follow-Ups					
				Cycle 1				Cycle 2		Subsequent Cycles		Cycle 1				Cycle 2			Subsequent Cycles	30-Day	Progression	Survival		
Day of cycle			-14 to-1	1	8	15	21	1	21	1		1	8	15	21	1	21	1						
												weeks												
Study Drug administration	D	6.1.2		Continuous daily dosing days 1-21 of each cycle then one week break																				
Adverse Events	D	8.1	Continuous from signed ICF up to 30 days after last dose of study treatment.																					
Prior/concomitant medications	D	6.3	Continuous from consent to 30-Day follow-up																					
Assessment of Patient Disposition	D	7.1.3	X								X								X					
Antineoplastic therapy since discontinuation	D	7.1.5.2																		X	X	X		
Survival Follow-up (telephone call/clinic visit every 12 weeks)	D	7.1.5.3																				X		

7.1.1 Screening

The Study IRB/IEC approved Informed Consent Form (ICF) must be signed and dated before any screening procedures are performed; however, procedures that are part of the clinical routine during the initial diagnostic work-up of the patient may be performed before signing the ICF. A copy of the ICF must be given to the patient (or patient's guardian as appropriate). The Investigator or designee must record the date when the study informed consent was signed in the medical records of the patient.

For patients under 18 years of age, consent will be obtained from parent(s) or legal guardian(s) and the signature of at least 1 parent or guardian will be required. Investigators will also obtain assent of minor patients according to local, regional or national guidelines.

The screening period starts once a patient has provided written informed consent to participate in the study and ends on the day of first dose of study drug. Screening assessments have to be completed within 14 days prior to the first dose of study drug except for imaging and hematologic laboratories. Baseline tumor imaging may be done up to 28 days prior and hematologic laboratories (ANC, platelet count, and hematocrit) up to 72 hours prior to first dose of study drug.

Abnormal laboratory values of potassium, magnesium or calcium correctable by oral supplementation must document a normalized laboratory value prior to randomization.

7.1.1.1 Eligibility screening

When the patient is considered eligible for study treatment, the study site should enter the information into the IRT/IVRS system to register and randomize the patient.

7.1.1.2 Information to be collected on screening failures

[figure not shown]
Patients who sign an informed consent but fail to start on study drug for any reason will be considered a screen failure. The reason for not starting study drug will be entered on the Screening Phase Disposition eCRF. The demographic information, informed consent, and Inclusion/Exclusion eCRF must also be completed for screen failure patients. No other data will be entered into the clinical database for patients who are screen failures, unless the patient experiences a Serious Adverse Event during the Screening Phase (See [Section 8](#) for SAE reporting details). The IRT must be notified within 2 days of the screen failure.

7.1.1.3 Patient demographics and other baseline characteristics

Baseline data on patient characteristics to be collected includes: general demographics, relevant medical history, cancer diagnosis, tumor burden, and prior medications and antineoplastic therapies.

7.1.2 Treatment period

During the treatment period, the patient must follow the Investigator's instructions with regards to contraception, concomitant medications, and dosing regimen (see [Section 6.1.1](#)). There is no fixed treatment duration. Patients may continue study drug until disease progression, unacceptable toxicity, discretion of the investigator or patient withdrawal of

consent. At time of documented progression per RECIST v1.1, patients may be unblinded and those randomized to placebo will be evaluated for crossover to LEE011. Patients should receive LEE011 within 28 days of the last radiological assessment. Safety labs and assessment are not required to be repeated for patients who start crossover C1D1 within 14 days of completing treatment. Patients initially randomized to the LEE011 arm may be permitted to continue on LEE011, despite progression, if the investigator documents ongoing clinical benefit for the patient in the source documentation, in a comment in the eCRF, and discussed decision with CPL. Please refer to [Section 4.1.6](#).

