7.1.3 Discontinuation of Study Treatment

Patients may voluntarily discontinue from the study or be discontinued from the study at the discretion of the investigator at any time. If a patient decides to discontinue from the study treatment, the investigator must make every effort (e.g. telephone, e-mail, letter) to determine the primary reason for this decision and record this information in the patient's chart and on the appropriate CRF pages. They may be considered withdrawn if they state an intention to withdraw, fail to return for visits, or become lost to follow-up for any other reason.

The investigator should discontinue study treatment for a given patient if he/she believes that continuation would be detrimental to the patient's well-being

If a patient discontinues study treatment, but continues study assessments, the patient remains on study until such time as he/she completes protocol criteria for ending study assessment. At that time, the reason for study completion should be recorded on the Study Phase Completion Disposition CRF page.

End of treatment/premature withdrawal visit is not considered as the end of the study.

Patients who prematurely discontinue study drug should be scheduled for a visit as soon as possible, at which time all of the assessments listed for the EOT visit will be performed ([Table 7-1](#)). This visit should take place no more than 14 days after the last dose of study drug. An EOT eCRF should be completed, giving the date and reason for stopping the study treatment. End of treatment/premature withdrawal visit is not considered as the end of study.

The investigator must contact the IRT to register the patient's discontinuation.

All patients who discontinue study drug should return for assessments according to [Table 7-1](#) including: safety follow-up ([Section 7.1.5.1](#)), disease progression follow-up (if applicable, [Section 7.1.5.2](#)) and survival follow-up ([Section 7.1.5.3](#)).

An End of Phase Disposition eCRF should be completed upon completion of the Disease Progression Follow-Up Period.

Patients may be discontinued from the study drug if any of the following occur:

- Patient withdrew consent
- Adverse event
- Lost to follow-up
- Death
- Non-compliance with study drug

- Physician decision
- Progressive disease
- Protocol deviation
- Study terminated by sponsor
- Technical problems
- Patient/parent/guardian decision

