7.2.2.5 Laboratory evaluations

The clinical laboratory analyses described below are to be performed by the sites local laboratory according to the time points indicated in [Table 7-1](#). More frequent assessments may be performed at the investigator's discretion if medically indicated and should be recorded on the Unscheduled Visit eCRF.

Abnormal laboratory values that are clinically relevant (e.g., require a dose modification and/or interruption of study drug, lead to clinical symptoms or signs, or require therapeutic intervention) must be documented in the Adverse Event eCRF.

Novartis must be provided with a copy of the site's local laboratory certification and tabulation of the normal ranges for each parameter required at study start and should be kept up to date on an ongoing basis if there are any changes. In addition, if at any time a patient has

laboratory parameters obtained from a different outside laboratory, Novartis must be provided with a copy of the certification and a tabulation of the normal ranges for that laboratory.

For all visits, there is a ± 3 days window on assessments to take into account scheduling over public or religious holidays if not explicitly specified otherwise. Laboratory assessments that were completed within 72 hours before Cycle 1, Day 1 (C1D1) do not need to be repeated.

Table 7-3 Local clinical laboratory parameters collection plan

Test Category	Test Name
Hematology	Hemoglobin, Platelets, Red blood cells, White blood cells with Differential (Basophils, Eosinophils, Lymphocytes, Monocytes, Neutrophils),
Chemistry	Albumin, Alkaline phosphatase, ALT (SGPT), AST (SGOT), Bicarbonate, Calcium, Chloride, Creatinine, Direct Bilirubin, Glucose, Indirect Bilirubin, Magnesium, Phosphate, Potassium, Sodium, Total Bilirubin, Total Protein, Blood Urea Nitrogen (BUN) or Urea
Coagulation	aPTT, Fibrinogen, INR ,PT
Thyroid	TSH; if indicated T3, T4 [free]
Pregnancy	Serum beta-HCG required at screening (only for women of child-bearing potential); subsequent testing may be serum or urine.

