7.2.2.5.5 Pregnancy and assessments of fertility

When highly effective contraception is required, pregnancy testing is required at screening and as indicated in [Table 7-1](#). At screening a serum pregnancy test must be performed. Urine or serum pregnancy tests are sufficient for all visits after screening.

Pregnancy tests are required at the following visits:

- Screening
- Day 1 of all cycles
- EOT Visit

If a patient becomes pregnant, the study drug must be stopped immediately. If a pregnancy test (urine or serum) is positive, but the patient is not thought to be pregnant the study drug should be held until it is determined that the test was false positive, and pregnancy is excluded. For females to be considered “of non-childbearing potential”, the patient must meet one of the following:

- Prior to onset of menarche (pre-menarche)
- Surgically sterile (have had surgical bilateral oophorectomy with or without hysterectomy) or tubal ligation at least six weeks before starting study drug. In case of oophorectomy alone, only when the reproductive status of the female has been confirmed by follow-up hormone level assessment.
- Post-menopausal and not of child bearing potential if they have had 12 months of natural (spontaneous) amenorrhea with an appropriate clinical profile (e.g., age appropriate, history of vasomotor symptoms).

To ensure patient safety, each pregnancy in a patient on study drug must be reported to Novartis within 24 hours of discovery. Pregnancy should be recorded on a Clinical Trial Pregnancy Form and reported by the investigator to the local Novartis Drug Safety and Epidemiology (DS&E). The pregnancy should be followed to determine outcome, including spontaneous or voluntary termination, details of the birth, and the presence or absence of any birth defects, congenital abnormalities, or maternal and/or newborn complications. Follow-up data should be recorded on the initial Clinical Trial Pregnancy Form and include an assessment of the possible relationship between any pregnancy outcome and the Novartis study drug. Any SAE experienced during pregnancy must be reported on the SAE Report Form.

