7.2.2.6 Cardiac assessments

7.2.2.6.1 Electrocardiogram (ECG)

A standard 12-lead ECG will be performed after the patient has been resting for 5-10 minutes prior to each time point indicated in [Table 7-4](#). At screening between Day -14 and Day -1, triplicate ECGs should be taken approximately 2 minutes apart. The combined QTcF values from these triplicate ECGs will be averaged to provide a single baseline value for each patient.

[REDACTED]

[REDACTED]

[figure not shown]
Each ECG tracing should be labeled with the study number, patient initials (where regulations permit), patient number, date, and kept in the source documents at the study site. Interpretation of the tracing must be made by a qualified physician and documented on the ECG eCRF. Each ECG tracing should be transmitted to a central laboratory and will be centrally reviewed by an independent reviewer. Clinically significant abnormalities at screening should be recorded on the relevant medical history/current medical conditions eCRF. Clinically significant findings must be discussed with Novartis prior to enrolling the patient in the study. New or worsened clinically significant findings occurring after informed consent must be recorded on the Adverse Events eCRF.

[figure not shown]
Table 7-4 ECG collection plan

[figure not shown]
Scheduled time points (hours)		
Screening		Anytime during the screening period
Cycle	Day	Sampling Time
1	1	Pre-dose
1	8	Pre-dose
1	8	2h post-dose (±30 min)
1	8	4h post-dose (±30 min)
1	15	Pre-dose
1	15	2h post-dose (±30 min)
1	15	4h post-dose (±30 min)
2	1	Pre-dose
2	21	Pre-dose
2	21	2h post-dose (±30 min)
3	1	Pre-dose
3	1	2h post-dose (±30 min)
4-5	1	Pre-dose
6	1	Pre-dose
6	1	2h post-dose (±30 min)
All other cycles ^a	1	Pre-dose
9 and every 3 rd cycle ^b	1	Pre-dose
9 and every 3 rd cycle ^b	1	2h post-dose (+/- 30 min)
Unscheduled		As clinically indicated
EOT		Within 14 days of last dose
^a Patients with QTcF ≥ 481 ms at any time prior to cycle 7; ^b Perform pre-dose ECG on the first day of every cycle. Additionally, 2 h post-dose in every 3 rd cycle (Cycle 9, 12, 15, 18 etc)		

[figure not shown]
[figure not shown]

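### Section 7.1.2 lets safety tests go unrepeated for 14 days before crossover, against Table 7-1 and the Day 1 and 72-hour rules; the effect is older pre-dose results in few if any patients

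*Protocol*

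**What the plan says.** Protocol Section 7.1.2 describes crossover from placebo after RECIST progression and adds: "Safety labs and assessment are not required to be repeated for patients who start crossover C1D1 within 14 days of completing treatment". It does not list the tests or define completion of treatment. The paragraph ends by referring to Section 4.1.6, which is redacted.

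Other parts of the protocol bear on the same visit:

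- **Table 7-1** marks hematology, chemistry, pregnancy test and ECG both at EOT and at crossover C1D1. All four come under Section 7.2.2, the protocol's own heading for safety assessments.
- **Section 7.2.2.5.5** requires pregnancy tests at screening, EOT and "Day 1 of all cycles", with no exception for crossover.
- **Section 7.2.2.5** has its own no-repeat rule for laboratory tests: "Laboratory assessments that were completed within 72 hours before Cycle 1, Day 1 (C1D1) do not need to be repeated".
- **Section 7.1.1** sets the entry windows: "Screening assessments have to be completed within 14 days prior to the first dose of study drug except for imaging and hematologic laboratories". The excepted blood counts have a tighter limit: "hematologic laboratories (ANC, platelet count, and hematocrit) up to 72 hours prior to first dose of study drug".
- **Section 7.1.3** on the EOT visit, which supplies the results that would not be repeated: "This visit should take place no more than 14 days after the last dose of study drug".

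**The concern.** For a placebo patient, crossover C1D1 is the first exposure to LEE011. The sponsor's own amendments record QTcF prolongation and possible liver injury (Amendment 2) and new teratogenicity data (Amendment 3). Pregnancy requires withdrawal from study drug (Section 7.1.3).

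Placebo should not have shifted these values. However, a patient crossing over under Section 7.1.2 has just progressed and may have started other medication. A site that follows Section 7.1.2 and a site that follows Table 7-1 would do different tests before the same dose. Under SAP Section 2.1.2.5, the crossover baseline is the last assessment before the crossover phase, so skipped Day 1 tests also make that baseline older.

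**Working it through.** The plan gives no figure to reproduce. The check is a comparison of rules, followed by simple day counts.

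**1. What Table 7-1 schedules.** The columns run: screening; Cycle 1 Days 1, 8, 15, 21; Cycle 2 Days 1, 21; later cycles Day 1; EOT; the same seven columns for crossover; crossover EOT. EOT is therefore the 9th column and crossover C1D1 the 10th. The hematology, chemistry and pregnancy rows are complete and carry a mark in both. The ECG row also has marks in the 9th and 10th positions, but is one cell short further right in the extracted text, so it is slightly less certain. Table 7-4 does list a pre-dose ECG on Cycle 1 Day 1. There is no crossover screening column. The eligibility check is marked at crossover C1D1, while coagulation and cardiac imaging are marked at EOT and not at crossover C1D1.

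**2. The rules side by side, at crossover C1D1.**

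| Source | Oldest acceptable result |
|---|---|
| Section 7.1.2 | 14 days, tests not named |
| Table 7-1 | test marked at the visit |
| Section 7.2.2.5.5 | pregnancy test on Day 1 |
| Section 7.2.2.5 | laboratory tests, 72 hours |
| Section 7.1.1 | blood counts, 72 hours; other screening tests, 14 days |

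The two 72-hour rows apply only if crossover C1D1 counts as C1D1, or as a first dose. Section 7.1.2 also limits the interval from the last scan to 28 days, so its 28- and 14-day limits match the entry windows in Section 7.1.1, but without the exception for blood counts.

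**3. Size.** Assume that EOT tests are done on or after the last placebo dose and before crossover. Nominal days are used and visit windows ignored.

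- Oldest result at the first LEE011 dose: tests on the day treatment is completed, crossover 14 days later, gives 14 days.
- Hematology and chemistry are next marked at crossover Day 15. Interval between draws with the waiver: 14 + (15 − 1) = 28 days. With a draw up to 72 hours before dosing: 3 + 14 = 17 days. Difference: 11 days.
- The pregnancy test is next marked at crossover C2D1. With the waiver: 14 + 28 = 42 days. With a Day 1 test: 28 days. Difference: 14 days.

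Both differences lie entirely before the first LEE011 dose. The 14 doses before the Day 15 draw and the 21 doses before the C2D1 pregnancy test are the same either way.

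**4. Reach.** The Amendment 3 study status gives 10 patients enrolled and 4 on treatment, of whom 3 are blinded and 1 has already crossed over. The ceiling for new crossovers is therefore three. With 2:1 randomization not all three need be on placebo, and their sex is not given.

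**The case against.** The strongest reply is that the sentence was meant only to let EOT stand in for a screening work-up. The matching 28- and 14-day limits support this, and at study entry a 14-day screening does not cancel the Day 1 tests. The specific pregnancy rule arguably overrides a general phrase. Eligibility is rechecked at crossover C1D1, and the criteria cover blood counts, liver tests, QTcF and pregnancy. Strong CYP3A inhibitors and drugs with a known QT risk are prohibited. Section 4.1.6 may say all this explicitly.

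Most of that stands as a likely intent, but Section 7.1.2 does not state it. The eligibility recheck does not say how old the values may be.

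A reader might infer more than the documents support:

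- **That the first LEE011 dose is given untested.** The word repeated presupposes earlier tests, EOT carries all four, and the waiver permits omission without forbidding the tests.
- **That 14 or 21 LEE011 doses go unmonitored because of the waiver.** Those doses come before the next scheduled tests in any case.
- **That three patients are affected.** Section 7.1.2 describes crossover after RECIST progression. Amendment 3 adds a route at the investigator's discretion, and the visible text does not show that the waiver applies to it.
- **That the protocol nowhere names the tests.** This is shown for Section 7.1.2 only, because Section 4.1.6 is redacted.

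**Conclusion.** The conflict is real on the face of the visible text. It is clearest against Table 7-1 and the Day 1 pregnancy rule, and conditional on how crossover C1D1 is counted for the 72-hour limits. Its size is an older pre-dose result: at most 14 days, instead of the same day or within 72 hours, in a patient coming off placebo. On-drug monitoring does not change, and few if any patients are affected.

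No efficacy result changes: under SAP Section 4, PFS and the secondary efficacy endpoints will not be analyzed. SAP Section 3 limits summary tables to the randomized phase, so an older crossover baseline could affect only listings. The conclusion rests on the extracted layout of Table 7-1, on EOT tests preceding crossover, and on Section 4.1.6 not already resolving the point. It is a low-priority improvement worth making because it is cheap.

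**What to change.** Replace the sentence in Section 7.1.2 with two:

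1. EOT results no more than 14 days old at crossover C1D1 may be used only for crossover eligibility items not scheduled at that visit, for example coagulation and cardiac imaging.
2. The tests marked at crossover C1D1 in Table 7-1 still apply: the Day 1 pregnancy test, the pre-dose ECG, and hematology and chemistry unless done within the previous 72 hours.

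Check Section 4.1.6 first and align the wording with it. The SAP needs no change. The cost is a repeat blood draw, pregnancy test and ECG at a visit that is already scheduled, for at most three patients.
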